10.4.5 Pharmacodynamic Data

A PK/PD analysis (PK/PD modelling) will be performed for triptorelin pamoate PR 3-month and triptorelin acetate PR 1-month exploring the relationship between plasma triptorelin concentrations and serum E_2 , FSH and LH, where possible.

Additional population PK/PD may be conducted. This analysis will be described in a separate data analysis plan and reported in a standalone report.

10.4.6 Efficacy Evaluation

10.4.6.1 Primary Efficacy Endpoint

The primary efficacy variable is the percentage of subjects castrated ($E_2 \leq 184$ pmol/L or 50 pg/mL) at Week 12.

The number and percentage of subjects castrated ($E_2 \leq 184$ pmol/L or 50 pg/mL) at Week 12 will be summarised by treatment group and the difference, including 2-sided 95% CI for the difference between treatment groups will be presented. If the lower limit of the 95% CI for the difference in percentage of subjects castrated ($E_2 \leq 184$ pmol/L or 50 pg/mL) at Week 12 between the triptorelin pamoate PR 3-month and triptorelin acetate PR 1-month is $>-10\%$, noninferiority of triptorelin pamoate PR 3-month will be confirmed.

10.4.6.2 Secondary Efficacy Endpoints

Percentage of Subjects Castrated ($E_2 \leq 184$ pmol/L or 50 pg/mL) at Weeks 4 and 8 and Percentage of Subjects Castrated ($E_2 \leq 110$ pmol/L or 30 pg/mL) at Weeks 4, 8 and 12:

The number and percentage of subjects castrated (according to each criterion) will be presented by treatment group for each visit. The difference between the treatment groups will be calculated and displayed with the 95% CI for the true treatment difference.

Change in Endometriosis-Associated Pelvic Pain (by 10 cm VAS) at Weeks 4, 8 and 12:

Endometriosis-associated pelvic pain measured by 10 cm VAS and change from baseline, will be summarised overall and for the subgroup of subjects with baseline VAS>3 cm at each time point, using summary statistics (n, mean, median, SD and minimum and maximum values) and the 95% CI for the true difference in mean VAS score and VAS change from baseline scores will be presented.

Serum E₂, FSH and LH Concentration at Weeks 4, 8 and 12:

Serum E₂, FSH and LH concentrations and change from baseline will be summarised at each time point, using descriptive statistics (n, mean, median, SD and minimum and maximum values) and the 95% CI for the difference between treatment groups in mean concentration values and mean change from baseline values will be presented for each parameter.

Time to Menses Recovery:

Time to menses recovery will be defined as the time (in days) between date of last dose of study drug and date of first day the subject observed menstrual bleeding of the next menstrual period. Any subjects withdrawing from the study without menstrual bleeding will be censored in the analysis at the date of withdrawal, and any subjects without menstrual bleeding prior to the end of study visit will be censored in this analysis at the date of the end of study visit.

The distribution of times to menses recovery will be estimated using the Kaplan-Meier method for each treatment group and presented graphically and median time to event and 95% CIs will be provided for each treatment group.

10.4.6.3 Exploratory Efficacy Endpoints**Percentage of Subjects Castrated 1) E₂≤184 pmol/L or 50 pg/mL 2) E₂≤110 pmol/L or 30 pg/mL at Week 24:**

The number and percentage of subjects castrated at Week 24 (according to each criterion) will be presented by treatment group. The difference between the treatment groups will be calculated and displayed with the 95% CI for the true treatment difference.

Change in Endometriosis-associated Pelvic Pain (by 10 cm VAS) at Weeks 16, 20 and 24 and the End of Study Visit Compared to Baseline:

Endometriosis-associated pelvic pain measured by 10 cm VAS and change from baseline, will be summarised overall and for the subgroup of subjects with baseline VAS>3 cm at each time point, using summary statistics (n, mean, median, SD and minimum and maximum values) and the 95% CI for the true difference in mean VAS score and VAS change from baseline scores will be presented.

Serum E₂, FSH and LH Concentration at Week 24:

Serum E₂, FSH and LH concentrations at Week 24 and change from baseline will be presented using summary statistics (n, mean, median, SD and minimum and maximum values) and the 95% CI for the difference between treatment groups in mean concentration values and mean change from baseline values will be presented for each parameter.

10.4.7 Adjustment for Centre Effect

Centre effect will be considered in analysis of the primary endpoint.

10.4.8 Safety Evaluation

All safety data will be included in the subject data listings. Analyses and summary tables will be based upon the safety set.

All AEs will be coded according to the Medical Dictionary for Regulatory Activities (MedDRA) version current at the start of the study, and will be classified by MedDRA preferred term and system organ class. AE listings will be presented by subject, system organ class and preferred term.

The incidence of all reported treatment-emergent adverse events (TEAEs) and SAEs will be tabulated by treatment group and overall. In addition, summary tables will be presented by maximum intensity, drug relationship and TEAEs associated with premature withdrawal of study medication.

A TEAE is defined as any AE that occurs from receiving the first dose of study drug to the end of study/early withdrawal visit if:

- it was not present prior to receiving the first dose of study drug, or
- it was present prior to receiving the first dose of study drug but the intensity increased during the active phase of the study.

All TEAEs will be flagged in the AE listings.

Prior and concomitant medication will be coded by using the World Health Organisation (WHO) Drug Dictionary (version December 2016 or above) and will be summarised separately by treatment group and overall with the number and percentage of subjects receiving prior and concomitant medication by drug class and preferred drug name. Prior medications/therapies are all those stopped prior to the first dose of study drug and concomitant medications/therapies are defined as all those ongoing or started at/after the first dose of study drug.

For laboratory data, abnormal values will be flagged in the data listings and a list of clinically significant abnormal values will be presented. Shift tables will be presented of the number and percentage of subjects with low, normal or high values and normal or abnormal physical/pelvic examination findings between baseline and Week 24 time points.

Vital signs data will be presented as shift tables, with the number and percentage of subjects with normal or abnormal findings between baseline and each assessment.

ECG data will also be presented as shift tables, with the number and percentage of subjects with normal or abnormal findings between baseline and Week 12 and Week 24.

Serum E₂, FSH and LH concentrations at Week 40 will be listed only.

Detailed methodology for the analysis of safety data will be presented in the SAP.

10.5 Subgroup Analyses

Endometriosis-associated pelvic pain and change from baseline will also be assessed at each timepoint for the subgroup of subjects with VAS>3 cm at baseline.

10.6 Interim Analyses

No interim analyses will be performed.

11 DIRECT ACCESS TO SOURCE DATA AND DOCUMENTS

Authorised personnel from external CAs and sponsor authorised Quality Assurance personnel may carry out inspections and audits. The purpose of an audit is to ensure that ethical, regulatory and quality requirements are fulfilled in all studies performed by the sponsor.

Auditors and inspectors must have direct access to study documents and site facilities as specified in Section 12.4, and to any other locations used for the purpose of the study in question (for example laboratories).

In the event of the site being notified directly of a regulatory inspection, the investigator must notify the sponsor's representative as soon as possible, to assist with preparations for the inspection.

12 QUALITY CONTROL AND QUALITY ASSURANCE

12.1 Protocol Amendments and Protocol Deviations and Violations

12.1.1 Protocol Amendments

No changes from the final approved (signed) protocol will be initiated without the prior written approval or favourable opinion of a written amendment by the IEC/IRB, except when necessary to eliminate immediate safety concerns to the subjects or when the change involves only logistics or administration. The principal investigator and the sponsor will sign the protocol amendment.

12.1.2 Protocol Deviations, Violations, and Exceptions

A protocol deviation is nonadherence to protocol-specific study procedures or schedules that does not involve inclusion/exclusion criteria, primary objective evaluation criteria, and/or GCP guidelines. Deviations are considered minor and do not impact the study.

A protocol violation is any significant divergence from the protocol, i.e. nonadherence on the part of the subject, the investigator, or the sponsor to protocol specific inclusion/exclusion criteria, primary objective evaluation criteria, and/or GCP guidelines. Protocol violations will be identified and recorded, by study centre personnel, on the eCRF.

As a matter of policy, the sponsor will not grant exceptions to protocol-specific entry criteria to allow subjects to enter a study. If under extraordinary circumstances such action is considered ethically, medically, and scientifically justified for a particular subject, prior approval from the sponsor and the responsible IEC/IRB, in accordance with the Standard Operating Procedure (SOP), is required before the subject will be allowed to enter the study. If investigative centre personnel learn that a subject who did not meet protocol eligibility criteria was entered in a study (a protocol violation), they must immediately inform the sponsor. Such subjects will be discontinued from the study, except in an exceptional instance following review and written approval by the sponsor and the responsible IEC/IRB, according to the applicable SOP.

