Subjects meeting the randomisation criteria will be allocated a randomisation number through an interactive web response system (IWRS) at baseline (Visit 2). This allocation will be performed in the order in which they enter the randomised study period and according to their endometriotic surgical history and severity of endometriosis-associated pelvic pain at baseline. The IWRS will assign subjects to one of two treatment groups based on a predefined randomisation list. A treatment number will be allocated by the IWRS each time drug is dispensed, according to the allocated treatment group. The IWRS will also manage all the logistical aspects of treatment (e.g. drug supplies; replacement of lost, damaged, quarantined, expiring or expired kits).

The investigator will under no circumstances change the randomisation number, the treatment number or the treatment arm allocated to the subject.

The IWRS will provide investigators, site coordinators and project team members with a 24-hour a day, 7-day a week service. Additional details may be found in the IWRS reference manual to be provided to each site. In case of technical, randomisation or dispensation queries, a 24-hour helpline will be available: see supporting information in the investigator site file.

Recruitment will stop once approximately 300 subjects have been randomised. Randomised subjects who terminate their study participation for any reason before starting the treatment will retain their randomisation number and treatment number (these numbers will not be reused). The next subject is given another randomisation number and another treatment number, even if she should receive the same treatment. Randomised subjects who leave the study early will not be replaced.

The sponsor's randomisation manager will keep the master randomisation list. A copy of this list will be confidentially supplied to the contract research organisation (CRO) in charge of the IWRS. The master list and the copy supplied to the CRO in charge of the IWRS will be kept confidential in a secure location. Access to the randomisation list must be restricted until authorisation is given to release it for final analysis.

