3.8 Maintenance of Randomisation and Blinding

The investigator will under no circumstances change the randomisation number and the treatment arm allocated to the subject via the IWRS. As this is an open-label study, there is no blinding of investigator or subjects.

To mitigate any potential bias due to the open-label design of this study, E₂, LH and FSH concentrations will be evaluated centrally.

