4.3 Subject Withdrawal Criteria and Procedures

In accordance with the Declaration of Helsinki, each subject is free to withdraw from the study at any time. The investigator also has the right to withdraw a subject from the study in the event of concurrent illness, AEs, pregnancy (see Section 8.1.5), or other reasons concerning the health or wellbeing of the subject, or in the case of lack of cooperation. In addition, a subject may be withdrawn from the study as described in Sections 3.6, 6.2 and 8.1.7.

Should a subject decide to withdraw from the study after administration of the IMP, or should the investigator decide to withdraw the subject, all efforts will be made to complete and report the observations up to the time of withdrawal as thoroughly as possible. A complete final evaluation at the time of the subject's withdrawal should be made (see Section 5.2.4.4) and an explanation given of why the subject is withdrawing or being withdrawn from the study.

The reason for and date of withdrawal from the study must be recorded on the eCRF. If a subject withdraws consent, every attempt will be made to determine the reason. If the reason for withdrawal is an AE or a clinically significant laboratory test abnormality, monitoring will continue until the event has resolved or stabilised, until the subject is referred to the care of a local health care professional, or until a determination of a cause unrelated to the IMP or study procedure is made. The specific AE or test result(s) must be recorded on the eCRF. All evaluations should be performed, according to the protocol, on the last day the subject receives IMP, or as soon as possible thereafter.

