10 STATISTICS

10.1 Analyses Sets

The following analysis sets will be used during statistical analyses:

- **Screened set:** All subjects screened (i.e. who signed the informed consent).
- **Randomised set:** All subjects randomised (i.e. who were randomly allocated to a treatment group).
- **Safety set:** All subjects who received at least one dose of study medication.
- **Full analysis set (FAS):** All randomised subjects who received at least one dose of study medication with at least one baseline and at least one post-baseline assessment of the primary efficacy parameter.
- **Per protocol (PP) set:** All subjects in the FAS for whom no major protocol violations/deviations occurred.
- **Full PK profile analysis set** (for noncompartmental analysis (NCA)): Subjects in the full PK/PD subgroup who have received at least one dose of IMP and have no major protocol deviations affecting the PK variables, and who have a sufficient number of PK concentration measurements to estimate the main PK parameters (maximum observed plasma concentration (C_{max}) and time to maximum observed plasma concentration (t_{max}), plus area under the plasma concentration-time curve for the dosing interval (AUC_{τ}) for subjects receiving triptorelin pamoate PR 3-month).
- **Sparse PK sampling analysis set:** All subjects who received at least one dose of IMP and have no major protocol deviations affecting the PK variables and who have at least one valid plasma concentration.
- **PD analysis set:** All subjects in the full PK/PD subgroup who have a sufficient number of PD measurements.
- **PK/PD relationships set:** All subjects who receive at least one dose of IMP and have at least one valid plasma triptorelin concentration and at least one PD measurement.

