10.1.2 Subject Allocation and Reasons for Exclusion from the Analyses

Any major protocol deviation types will be described in the Protocol Deviation Document (PDD) and their impact on inclusion in each analysis set for any subject will be specified. The final list of protocol deviations impacting each analysis set will be reviewed during the blind data review meeting held prior to database lock, without reference to treatment group assignment for individual subjects.

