7.7.1 Adverse Events

A treatment-emergent adverse event (TEAE) is defined as any AE that occurs or worsens on or after the first dose of IMP, through 112 days (16 weeks) after last injection for triptorelin pamoate PR 3-month groups or through 56 days (8 weeks) after injection for triptorelin acetate PR 1-month group. Non-TEAEs and TEAEs will be separately summarised in tables and all AEs will be presented in the listing with flag of TEAE status.

All adverse events (AEs) recorded on the eCRF will be coded to SOC and PT using the MedDRA dictionary (version number is the newest version used in Covance coding system at the time of analysis). A subject will be counted at most once within a SOC and PT in summary tables.

In the summary table of TEAEs, the numbers and percentages of subjects and events will be tabulated and presented by treatment groups and overall for the following categories:

- Any TEAEs
- TEAEs with maximum intensity (Severe, Moderate, Mild)
- Serious TEAEs
- Drug-related TEAEs
- Drug-related serious TEAEs
- TEAEs leading to drug withdrawal
- TEAEs leading to drug interruption
- Serious TEAEs leading to drug withdrawal
- Serious TEAEs leading to drug interruption
- TEAEs leading to death

The numbers and percentages of subjects and events will be also be separately summarised by SOC and PT (sorted alphabetically) for each treatment group and overall as the above AE categories. The TEAEs with intensity of Severe will be separately summarised by SOC and PT (sorted alphabetically) for each treatment group and overall. The TEAEs and drug-related TEAEs will be also separately summarised by maximum intensity, SOC and PT (sorted alphabetically) for each treatment group and overall.

TEAEs or drug-related TEAEs with PTs observed $\geq 5\%$ or $\geq 10\%$ of subjects in any one of the treatment groups will be separately summarised by SOC and PTs.

In the event of multiple events being reported by the same subject, the maximum intensity (severe, missing, moderate, mild) and the most serious causality (related, not related) will be chosen. If severity is missing for one event and the subject had no intensity of severe in the same category events, “missing” row should be added after severe in the summary tables with maximum intensity.

Statistical Analysis Plan

Version: Final 3.1

Ipsen Pharma; Protocol No. D-CN-52014-220

Date of Issue: 13DEC2019

CCI

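### Protocol 12.1.2 takes women found ineligible after entry out of the study, not only off drug, so a dosed woman removed before Week 12 has no primary-endpoint sample

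*Protocol*

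**What the plan says.** Protocol 12.1.2 requires a site that learns an ineligible woman was entered to tell the sponsor at once. It continues: "Such subjects will be discontinued from the study, except in an exceptional instance following review and written approval by the sponsor". Ethics committee approval is needed too, under an operating procedure that is not reproduced, and the protocol gives no criteria for the exception. The rule makes no distinction between dosed and undosed women, or between ending treatment and ending participation.

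Other provisions that bear on it:

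- **Replacement (Protocol 3.3):** "Randomised subjects who leave the study early will not be replaced".
- **FAS (Protocol 10.1; SAP 5.4):** "All randomised subjects who received at least one dose of study medication with at least one baseline and at least one post-baseline assessment". The assessment meant is E2. Ineligibility is not a ground for exclusion.
- **Per-protocol set (SAP 5.5):** FAS members who have a Week 12 measurement and no major deviation affecting the primary endpoint. This is the primary analysis population.
- **Missing E2 (SAP 6.2):** the last available post-baseline value is carried forward to derive castration.
- **Deviation review (Protocol 10.1.2):** deviations that affect analysis sets are reviewed at a meeting "held prior to database lock, without reference to treatment group assignment for individual subjects".
- **Withdrawal (Protocol 4.3):** "A complete final evaluation at the time of the subject's withdrawal should be made". Section 5.2.4.4, however, lists E2 at the end-of-study or early-withdrawal visit only when menses has not recovered before Week 40.
- **Blinding (Protocol 3.8):** "there is no blinding of investigator or subjects".

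**The concern.** Followed exactly, the rule creates missing primary-endpoint data that the trial could have collected. The visits are already scheduled, the drug has been given, and the analysis plan already deals with ineligibility through the per-protocol criteria.

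The order of events also matters. The plan's safeguard against selective exclusion is a review done without reference to individual treatment assignment. Removal under 12.1.2 happens earlier, at a time when the site knows the arm, and the later review cannot restore a sample that was never taken. At stake are the completeness of the per-protocol set and the value of the FAS as an as-randomised check on it in a non-inferiority comparison.

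**Working it through.** **1. The plan's own figure.** Inputs from Protocol 10.2: castration rate 92% (taken as equal in both arms), margin 10 points, one-sided alpha 0.025, power 85%.

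n per arm = (1.960 + 1.036)² × 2 × 0.92 × 0.08 / 0.10² = 132.2, rounded up to 133. This matches the plan. Power at 133 is 85.2%. Inflating for 10% dropout, 133 / 0.90 = 147.8, so 148 per arm or 296 in total; 300 covers it.

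**2. What happens to a removed, dosed woman, by time of removal.**

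| Removal | Week 12 E2 | Per-protocol set | FAS |
|---|---|---|---|
| Before any post-baseline E2 | none | out | out |
| After a post-baseline E2, before Week 12 | none | out, whatever the breach | in, scored on the earlier value |
| After the Week 12 sample | present | decided by the deviation criteria | in, own value |

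Three qualifications apply:

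- Most women have their first post-baseline E2 at Week 4. The PK/PD subgroup (up to 32 women) is also sampled at Weeks 1, 2 and 3, so removal before Week 4 does not always mean absence from the FAS.
- SAP 6.1 re-maps an early-withdrawal visit to Week 12 only on Days 82-109, and Protocol 5.2.4.4 leaves it unclear whether E2 is taken at that visit at all.
- Carrying forward is not the same in the two arms. At Weeks 4 and 8 the 1-month sample is predose, at the end of its 4-week interval. The 3-month sample at those visits falls within its 12-week interval, and only the Week 12 predose sample shows the end of it (Protocol 3.1 and 5.2.3).

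**3. Size.** The documents give no rate of late-found ineligibility. Assume 2-5% of 300, which is 6-15 women, or 3 to 7.5 per arm. This is an upper bound for lost Week 12 values, because only removals before that visit count. With 150 per arm, less 10% dropout and a further fraction f removed:

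n = 150 × (0.90 − f); power = Φ(0.10 / √(2 × 0.92 × 0.08 / n) − 1.960)

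| f | n per arm | Power |
|---|---|---|
| 0 | 135 | 85.7% |
| 2% | 132 | 85.0% |
| 3% | 130.5 | 84.6% |
| 5% | 127.5 | 83.7% |

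Power is hardly affected.

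**4. What selection could do, as an illustration only.** Take 135 per arm with true rates exactly at the margin, 82% against 92%. The expected number castrated in the 3-month arm is 0.82 × 135 = 110.7. Removing x non-castrated women from that arm alone gives a difference of 110.7 / (135 − x) − 0.92:

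| x | Difference (points) |
|---|---|
| 0 | −10.0 |
| 1 | −9.4 |
| 2 | −8.8 |
| 3 | −8.1 |
| 5 | −6.8 |

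This is a worst case in which every removal is from one arm and every removed woman is a failure. It shows how sensitive the comparison is to a handful of women. It is not an estimate of bias.

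**The case against.** The strongest reply is that the trigger is a baseline fact, checked at screening and again before randomisation, so late findings should be few. E2 is measured centrally. No mechanism is evident by which detection would differ by arm or follow the E2 result. In the per-protocol set, a breach judged to affect the endpoint would exclude the woman anyway. In the FAS, most removed women stay in through carry-forward. All of this stands, and it limits the size of the point. It does not answer the woman whose breach is harmless to the endpoint and who is still lost to the primary set, or the woman removed before any post-baseline E2.

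A reader might infer more than the documents support:

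- **That removal is a discretionary, unblinded decision.** Removal is the default. Only retention is discretionary, and it needs ethics committee as well as sponsor approval. The site knows the arm, but nothing says the approvers are shown arm or E2 results, although nothing prevents it either.
- **That safety follow-up is lost.** It is shortened. The scheduled visits end, but the withdrawal evaluation (4.3, 5.2.4.4), follow-up of persisting adverse events (8.1.3), later reporting of suspected related events (8.1.4) and pregnancy reporting to 150 or 90 days after the last dose (8.1.5) all remain.
- **That the rule contradicts the SAP's adverse-event window.** SAP 7.7.1 counts events "through 112 days (16 weeks) after last injection for triptorelin pamoate PR 3-month groups", or 56 days for the 1-month arm. That classifies events and does not set visits. For women dosed on schedule both windows end about Day 197 (85 + 112 and 141 + 56), and a completer whose menses returns soon after Week 24 may have her last visit before then.
- **That 2-5% removed means 2-5 points of bias against the 10-point margin.** Missing values are not bias. Bias needs removal related to both arm and outcome, which is not shown.

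**Conclusion.** The point holds as a modest, cheaply corrected design weakness. Section 12.1.2 merges stopping drug with leaving the study. By rule, that costs the Week 12 E2 of any dosed woman removed before that visit, and it acts ahead of the review that is meant to decide exclusions without reference to arm.

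On an assumed 2-5% rate, at most 6-15 women are affected and the loss of power is 0.7 to 2.0 points (85.7% to 85.0-83.7%), so power is not the reason to act. The reason is avoidable missing primary-endpoint data and room for selection in an open-label non-inferiority trial. The planned sample size reproduces and need not change. The conclusion on size rests on the assumed rate and the normal approximation. The wording problem depends on neither.

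**What to change.** Amend Protocol 12.1.2 to say, in substance:

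- A randomised, dosed woman found not to have met an eligibility criterion remains in the study for the scheduled assessments, including the Week 12 E2 sample, adverse events and menses status, unless she withdraws consent. This applies irrespective of whether study drug continues.
- She stays in the FAS as randomised, under its existing definition.
- Her per-protocol status is settled by the criteria listed in advance in the protocol deviation document, at the data review described in 10.1.2.

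Separately, reconcile Protocol 4.3 with 5.2.4.4 so that it is clear whether E2 is taken at an early-withdrawal visit.

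Whether further study drug is given, and who decides, is a clinical matter. Nothing is proposed on it, and the change does not depend on it.

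The cost is amendment wording. The visits are already scheduled for every randomised woman and the sample size is unchanged. The downside is that a few ineligible women contribute Week 12 data to the FAS, which its definition already allows.
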